## **10.5 Interim Analyses**

Safety Assessments will be completed periodically, and at the end of the registry, on all cumulative data at specific time points. The timing and content of the interim safety assessments will be based on decisions from Regulatory Agencies, from the Steering Committee meetings and the Publication Plan. Effectiveness analyses may also be included in the Interim Reports as deemed appropriate.

## **10.6 Determination of Sample Size**

The proposed sample size for this registry is approximately 800 patients. Due to the low incidence and prevalence of the disease, the size of the registry has been chosen based on the expected availability of eligible patients to be enrolled in a three year time frame. The estimated recruitment rates were based on published articles and advice from one leading pediatric rheumatology site.

It is planned that a total of 800 patients will be enrolled to this registry in a ratio of 5:3 corresponding to the Humira arm or the MTX arm respectively. The sample size determination is based on the rate of serious infectious AEs in the Humira arm. Assuming a total of 500 patients with full 5 years of follow up in the Humira arm, a maximum total exposure to the Humira in this registry can be 2500 patient years. Typically a higher rate of dropout is expected in a registry compared to traditional controlled studies. Allowing for approximately 68% dropout, a total of approximately 1500 patient years exposure in the Humira arm will have approximately 97% power, using a two-sided test at level of significance  $\alpha = 0.05$ , to detect a rate of serious infectious AE of 4.8 events per 100 patient years from the rate of 2.8 events per 100 patient years previously seen in this population in Study DE038.

Due to low frequencies of malignancies and congestive heart failure (CHF), patients will be followed for an additional 5 years.

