## **6.1 Selection of Population**

Once a decision has been made between the physician and the patient to use Humira (monotherapy or combination therapy with MTX) or MTX (without Humira) as part of usual care for and in accordance with approved local prescribing information for polyarticular JIA, sites will be encouraged to offer enrollment to all eligible patients. After a decision to prescribe Humira, patients from previous Humira clinical trials (Study M10-444 and Study DE038) will be offered enrollment in the registry. Prior to collecting registry-related information, a parent or legal guardian must sign a parental consent and patient assent/authorization form, or appropriate forms per local requirements for release of information. Physicians should determine the appropriate therapy for each patient without regard to study participation. The participating physician will provide the patient a prescription for Humira (monotherapy or combination therapy with MTX) or MTX (without Humira) along with instructions for appropriate use in patients with moderately to severely polyarticular JIA.

Patients prescribed Humira rolling over from another AbbVie clinical study will continue in the Humira arm.

New patients may be enrolled in one of two arms, the Humira arm or the MTX arm, depending on the treatment decision made by the physician prior to enrollment.

Patients in the Humira arm may be treated with Humira alone or in combination with MTX.

Patients in the MTX arm may be treated with MTX alone or in combination with other DMARDs, but not with anti-TNFs or other biologic therapies.

Patients who are non-responders, intolerant to MTX treatment arm or are in need of combination treatment with Humira therapy are eligible to switch to the Humira treatment arm up until enrollment of the last patient into the registry (i.e., until enrollment in the Humira treatment arm is complete).

In these cases patients will be required to discontinue from the MTX arm and consent as a new patient in the Humira arm once any Adverse Events of Special Interest and SAEs have been resolved or the AbbVie Study Designated Physician should be contacted to assess the eligibility of a patient to enroll in the Humira treatment arm if an AE is ongoing and eligibility criteria are met.

The 10-year follow-up time for these patients begins when these patients start the Humira arm and not the date they started the registry within the MTX arm.

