### 6.1.1 Inclusion Criteria

The decision to prescribe either Humira or MTX must be made prior to the decision to enroll a patient in the registry. A patient will be eligible for participation if he/she meets the following criteria:

1. For a patient enrolling into the Humira arm; a pediatric patient diagnosed at any time with moderately to severely active polyarticular or polyarticular-course JIA (defined as arthritis affecting ≥ 5 joints at the time of diagnosis of polyarticular or polyarticular-course JIA) who has been prescribed Humira therapy according to the locally approved Humira product labeling and meets one of the following criteria:
  - a. Enrolled patients are 4 to 17 years of age as per approved Humira product label with the addition of polyarticular JIA patients 2 to < 4 years of age in countries with available local approval for this group of patients at the time of consent to the registry.
  - b. Newly initiated (within 24 months of registry entry) on Humira therapy and has received continuous (no more than 70 consecutive days off drug) Humira therapy, and the physician can provide available source documentation of SAEs, AEs of Special Interest, and dosing information since initiation of therapy;
  - c. Or is entering after participation (within 24 months of registry entry or, if longer, continuously treated at the same site) in an AbbVie Humira sponsored study, regardless of age or the number of joints with symptoms of polyarticular JIA, and has received continuous (no more than 70 consecutive days off drug) Humira therapy and the physician can provide available source documentation of SAEs, AEs of Special Interest, and dosing information since initiation of therapy.
2. For a patient enrolling into the MTX arm; a pediatric patient diagnosed at any time with moderately to severely active polyarticular or polyarticular-course JIA (defined as arthritis affecting ≥ 5 joints at the time of diagnosis of polyarticular or

polyarticular-course JIA) who is prescribed MTX therapy alone or in combination with other DMARDs according to the local product labeling (initiated treatment within 24 months of registry entry) and has received continuous therapy and the physician can provide available source documentation of SAEs, AEs of Special Interest, and dosing information since initiation of therapy.

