### **10.3.2 Analysis of Registry Treatment-Emergent SAEs and AEs of Special Interest**

Registry Treatment-emergent SAEs and AEs of Special Interest will be summarized.

Registry Treatment-emergent AEs includes AEs occurring from the first dose day of the registry to 70 days after the last dose of registry drug excluding AEs occurring during TI period. The SAEs and AEs of Special Interest collected through the HCP process will not be included in this summary.

The number and percentage of patients experiencing registry treatment-emergent SAEs and AEs of Special Interest will be tabulated by body system and MedDRA® preferred

term. In addition, a summary of SAEs and AEs of Special Interest by severity and relationship to registry drug will be presented. Rates (event per 100 patient-years of registry exposure to Humira or MTX) of SAEs and AEs of Special Interest and the 95% confidence interval will be provided.

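### Study DE038 supplies the 2.8 per 100 patient-year benchmark, yet its roll-overs enter the Humira arm and are pooled in the safety rates, which may mask an excess in routine-care patients

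*Supplement*

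**What the plan says.** Section 10.6 (Determination of Sample Size) contains the protocol's only quantified safety comparison. It says that about 1500 patient-years on Humira "will have approximately 97% power", with alpha set at 0.05 and two-sided. The alternative of interest is "a rate of serious infectious AE of 4.8 events per 100 patient years". The reference value it departs from is the earlier trial's: "from the rate of 2.8 events per 100 patient years previously seen in this population in Study DE038".

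Section 6.1 states that "patients from previous Humira clinical trials (Study M10-444 and Study DE038) will be offered enrollment in the registry", and places roll-overs who are prescribed Humira in the Humira arm. Inclusion criterion 1c (section 6.1.1) admits patients from a sponsored Humira study "within 24 months of registry entry or, if longer, continuously treated at the same site". It does so, as a separate clause puts it, "regardless of age or the number of joints with symptoms of polyarticular JIA". They must have had no gap of more than 70 consecutive days off drug. Criterion 1b admits commercial Humira patients up to 24 months after starting, and criterion 2 has the same 24-month window for methotrexate.

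Section 10.1 defines a single All Treated Population for safety. Section 10.3.1 gives observational rates from the first registry day. Section 10.3.2 gives on-treatment rates within the registry: "Registry Treatment-emergent AEs includes AEs occurring from the first dose day of the registry to 70 days after the last dose". Section 10.3.3 counts from the first recorded dose, including on-drug time in the earlier study for roll-overs. All three plan rates per 100 patient-years with 95% confidence intervals, and none is split by entry route.

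**The concern.** The primary objective is the long-term safety of Humira in routine clinical practice. The cohort that produced the benchmark can re-enter the arm that will naturally be set beside it. Those who re-enter are the ones who tolerated continuous treatment, in some cases for years, because the same-site clause puts no fixed limit on prior exposure. Patients who stopped early, for infection or any other reason, cannot enter by this route.

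If long-term continuers have fewer serious infections than patients treated outside a trial, the pooled rate averages the two. An excess among routine-care patients could then look smaller than it is, and the registry would be less able to show the increase it was sized for. The methotrexate arm has no roll-over route, so the two arms also differ in how much of their person-time comes from long-term continuers.

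**Working it through.** **Inputs from section 10.6:** benchmark 2.8 and alternative 4.8 per 100 patient-years; 1500 patient-years; two-sided alpha 0.05; stated power about 97%; 500 Humira patients; about 68% dropout over 5 years.

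**Reproducing the plan.**
- Exposure, assuming exponential dropout: hazard = −ln(0.32)/5 = 0.2279 per year, so 500 × 0.68/0.2279 = 1492 patient-years, close to the stated 1500.
- Expected events: 15 × 2.8 = 42 at the benchmark and 15 × 4.8 = 72 at the alternative.
- Exact Poisson test: the smallest k with P(X ≥ k | 42) ≤ 0.025 is 56 (tail 0.0223). Power = P(X ≥ 56 | 72) = 97.8%.
- Score approximation: Φ((72 − 42 − 1.96√42)/√72) = 97.9%. The stated figure reproduces.

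**Effect of pooling.** Let f be the roll-over share of Humira-arm person-time and r their serious-infection rate. The protocol gives neither, so both are assumptions. If all other patients run at 4.8, the arm rate is m = (1 − f) × 4.8 + f × r, and exact power is P(X ≥ 56 | 15m).

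| f | r = 2.0 | r = 2.8 | r = 3.8 | r = 4.8 |
|---|---|---|---|---|
| 10% | m = 4.52, 93.6% | m = 4.60, 95.2% | m = 4.70, 96.7% | 97.8% |
| 20% | m = 4.24, 84.5% | m = 4.40, 90.5% | m = 4.60, 95.2% | 97.8% |
| 30% | m = 3.96, 68.8% | m = 4.20, 82.7% | m = 4.50, 93.1% | 97.8% |

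With r = 2.8, power falls below 90% at a share of about 21% and below 80% at about 33%.

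**What is known about the share.** Section 3.0 reports 228 patients across three earlier Humira JIA studies, one of which (M10-240) section 6.1 does not name as a roll-over source. 228/500 = 45.6% is therefore only a loose ceiling on the share of patients. The true share will be lower, because entry requires continuous treatment and consent. Section 6.4 expects 40 to 45 of about 120 physicians to come from earlier Humira JIA studies, so the route is not obviously negligible.

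**Restricting to non-roll-overs at a rate of 4.8** (1500 × (1 − f) patient-years, exact test against 2.8):

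| f | Patient-years | Reject at | Power |
|---|---|---|---|
| 10% | 1350 | 51 or more | 96.6% |
| 20% | 1200 | 46 or more | 94.9% |
| 30% | 1050 | 41 or more | 92.2% |

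This beats pooling when r is 2.8 or 2.0. It is about equal or slightly worse when r = 3.8, and it loses power when r = 4.8 (pooled 97.8%). Neither analysis dominates, so both should be shown.

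**Where earlier-study data enter.** Sections 10.3.1 and 10.3.2 count registry time only. Section 10.3.3 also counts roll-overs' on-drug events from the earlier study, leaving out the DE038 double-blind period for those on placebo. Only there can events from DE038 itself be counted again.

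**The case against.** The strongest objections, and what stands of each:

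- **The direction is not demonstrated.** A reader might infer that roll-overs do pull the registry rate towards 2.8. The documents do not support that. It needs a lower rate in roll-overs and a material share of person-time, and neither is given. Selection on continued treatment makes a lower rate plausible, and it could even lie below 2.8. This stands: the pull is a possibility.
- **The largest losses rest on an assumed rate.** The rate of 2.0 appears nowhere in the protocol. With roll-overs at 2.8, power stays above 80% up to a 30% share, and at a 10% share restriction gains only 1.4 points (96.6% against 95.2%). This stands as a limit on size.
- **There is no test to distort.** Section 10.3 plans descriptive rates with intervals, and 2.8 appears only in section 10.6, which also says size was driven by patient availability. This stands. The rates will nonetheless be read against the figure that sized the registry.
- **A reader might infer that DE038 is being compared with itself.** In sections 10.3.1 and 10.3.2 the person-time is new and only the patients are shared. The phrase is literal only for section 10.3.3.
- **Late entry is partly handled, and is not confined to Humira.** Section 10.3.3 counts from the initial dose, and the methotrexate arm has the same 24-month window. Both are true. Counting back does not undo the selection of patients who stayed on treatment long enough to enroll, and the roll-over route remains specific to the Humira arm.
- **Follow-up continues past five years.** Serious adverse events are reported through Year 10. If the same dropout continued (an assumption), exposure would be about 1970 patient-years, and power at r = 2.0 and f = 30% would be 80% rather than 69%. This softens the worst case.
- **The split may be left to the SAP, which is not shown.** That is possible. But the protocol itself specifies pooled rates and sets out other safety subgroups in detail (section 10.3.4, by treatment interruption), so entry route can reasonably be named there too.

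**Conclusion.** The concern holds in a limited form. The benchmark comes from DE038, DE038 and M10-444 patients still on Humira enter the Humira arm, and the planned safety rates do not separate them. Pooling may lower the registry rate and mask an excess in routine-care patients.

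The size cannot be fixed from the protocol. It ranges from nothing, if roll-overs have the same rate as everyone else, through a few points of power at a 10% share, to a fall from 97.8% to 83% at a 30% share with roll-overs at 2.8. These figures assume 1500 patient-years, a one-sample exact Poisson comparison and a true rate of 4.8 in all other patients. They illustrate sensitivity and do not describe a test that the plan will run. The sample-size calculation itself is sound on its own inputs.

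**What to change.** In sections 10.3.1 to 10.3.3, keep the pooled rates and add the following, each with 95% confidence intervals:

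- rates of serious adverse events, events of special interest and serious infections by entry route: roll-over from DE038 or M10-444; commercial Humira started before enrollment; Humira started at enrollment;
- the same rates by time since first Humira dose, for example up to 6 months, 6 to 24 months and over 24 months;
- the methotrexate rates by time since first methotrexate dose.

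Show any reading against 2.8, or against the methotrexate arm, for non-roll-over patients beside the pooled result, without replacing it. Non-roll-overs still include patients already on commercial Humira under criterion 1b, so the split by time since first dose is needed as well. Report each route's share of person-time, so that the reader can judge how much pooling matters.

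The cost is a few sentences in the plan and a stratified table. No new data are needed: the prior-study patient number is recorded under section 6.6.1, retrospective exposure is requested under section 6.6.2, and section 10.2 already uses the first recorded dose. The downside is fewer patient-years and wider intervals in each subset, and some loss of power in the restricted comparison if roll-overs in fact have the same rate as other patients.

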## **11.0 Final Report and Publications**

### **11.1 Use of Information**

At the end of the registry, a final registry report will be written. This report will contain a description of the objectives of the registry, the methodology of the registry and its results and conclusions. The completed CRFs and the registry report must be treated as the confidential property of AbbVie and may not be released to unauthorized people in any form (publications or presentations) without express written approval from AbbVie. The results of this registry may be published by AbbVie or by any one of the participating physicians after agreement with AbbVie.

### **11.2 Internet Sites**

Information regarding this registry may be posted on various internet websites and will maximally include registry name, number, general population to be enrolled, entrance qualifications, brief description of the registry, registry objectives, doses, accruing physicians (upon their approval) and number of patients to be enrolled.

## **12.0 Completion of the Registry**

AbbVie will select the signatory Investigator from the Investigators who participate in the registry. Selection criteria for this Investigator will include level of participation as well as significant knowledge of the clinical research, investigational, (non interventional Registry) drug and the registry protocol. The signatory Investigator for the registry will review and sign the final report in accordance with the EMA Guidance on Investigator's Signature for Study Reports.

The end-of-registry is defined as the date of the last patient's visit in the registry or direct to HCP process, whichever occurs later.

The Physician will conduct this registry in compliance with the protocol and all applicable regulatory and legal requirements. AbbVie may terminate this registry at any time, either in its entirety or at a site, for reasonable cause provided that written notice is submitted at

a reasonable time in advance of the intended termination. The Physician may also terminate the registry at their site for reasonable cause, after providing written notice to AbbVie a reasonable time in advance of the intended termination.

## Appendix A. List of Abbreviations and Definition of Terms

### Abbreviations

aCL	Anticardiolipin Antibodies
ACR	American College of Rheumatology
AE	Adverse Event
AESI	Adverse Events of Special Interest
ANA	Antinuclear Antibody
AS	Ankylosing Spondylitis
BD	Beçhet's Disease
CHF	Congestive Heart Failure
CHQ	Child Health Questionnaire
CPK	Creatine Phosphokinase
CRF	Case Report Form
CRO	Contract Research Organization
CRP	C-reactive Protein
CTC	Common Toxicity Criteria
DICHAQ	Disability Index of Childhood Health Assessment Questionnaire
DMARD	Disease-modifying Antirheumatic Drug
eCRF	Electronic Case Report Form
EMA	European Medicines Evaluation Agency
ERA	Enthesitis-Related Arthritis
eSAE	Electronic Serious Adverse Event
ESR	Erythrocyte sedimentation rate
EU	European Union
FDA	Food and Drug Administration
GCP	Good Clinical Practices
HCP	Health Care Provider
HS	Hidradenitis Suppurativa
ICH	International Conference on Harmonization
IEC/EC	Independent Ethics Committee/Ethics Committee
IL	Interleukin
IRB	Institutional Review Board
ITT	Intent-to-treat

JIA	Juvenile Idiopathic Arthritis
JRA	Juvenile Rheumatoid Arthritis
LA	Lupus Anticoagulants
LOM	Limitation of Passive Motion
MedDRA	Medical Dictionary for Drug Regulatory Activities
MTX	Methotrexate
nr-axSPA	Non-radiographic axial spondyloarthritis
NSAID	Nonsteroidal Anti-inflammatory Drug
PedACR	Pediatric ACR
PMOS	Post-marketing Observational Study
POM	Pain on Passive Motion
Ps	Psoriasis
PsA	Psoriatic Arthritis
RA	Rheumatoid Arthritis
RF	Rheumatoid Factor
SAE	Serious Adverse Event
SAP	Statistical Analysis Plan
SDCF	Supplemental data clarification form
TB	Tuberculosis
TNF	Tumor Necrosis Factor
UBC	United BioSource Corporation
UC	Ulcerative Colitis
ULN	Upper Limit of Normal
US	United States
VAS	Visual Analog Scale

**Appendix B. List of Protocol Signatories**

## **Appendix C. Responsibilities of the Clinical Investigator**

Clinical research studies sponsored by AbbVie are subject to the regulations of the U.S. Food and Drug Administration (FDA). The responsibilities imposed upon Investigators by the FDA are summarized in the "Statement of Investigator" (Form FDA 1572), which is a form letter addressed to the sponsor (AbbVie), summarizing the Investigator's qualifications for the registry and his/her willingness to follow FDA regulations with respect to the registry.

In signing a Form FDA 1572, the Investigator agrees to assume the following responsibilities:

1. To conduct the registry(ies) in accordance with the relevant, current protocol(s) and only make changes in a protocol after notifying AbbVie, except when necessary to protect the safety, rights, or welfare of subjects.
2. To personally conduct or supervise the described investigation(s).
3. To inform any subjects, or any persons used as controls, that the drugs are being used for investigational purposes and to ensure that the requirements relating to obtaining informed consent in 21 CFR Part 50 and Independent Ethics Committee (IEC)/Institutional Review Board (IRB) review and approval in 21 CFR Part 56 are met.
4. To report to AbbVie adverse experiences that occur in the course of the investigation(s) in accordance with 21 CFR 312.64.
5. To read and understand the information in the Investigator's Brochure, including the potential risks and side effects of the drug.
6. To ensure that all associates, colleagues, and employees assisting in the conduct of the registry(ies) are informed about their obligations in meeting the above commitments.

7. To maintain adequate and accurate records of the conduct of the registry and make those records available for inspection by representatives of AbbVie, the IRB and/or the appropriate regulatory agency, and to notify AbbVie when no longer able to retain the registry-related documents.
8. To ensure that an IEC/IRB that complies with the requirements of 21 CFR Part 56 will be responsible for the initial and continuing review and approval of the clinical investigation.
9. To promptly report to the IEC/IRB all changes in the research activity and all unanticipated problems involving risks to human subjects or others (including submission of any Expedited Safety Reports received from AbbVie to the IEC/IRB), and to make no changes in the research without IEC/IRB approval, except where necessary to eliminate apparent immediate hazards to human subjects.
10. To comply with all other requirements regarding the obligations of Clinical Investigators and all other pertinent requirements in 21 CFR Part 312.

